4. SUBJECT POPULATION

Subjects 18 years and older with advanced or metastatic NSCLC who had at least 2 cycles of standard platinum-based therapy with disease progression or intolerance to therapy will be eligible for this study.

An optional Prescreening informed consent will be offered for the purpose of testing archival tumor tissue to assess PD-L1 status using the SP142 assay (Section 9.1.2) to help determine the likelihood of eligibility for participation in this study. However, final eligibility for study participation will be based on PD-L1 staining on the fresh biopsy required during the Screening Phase, unless the archival tumor sample used in the Prescreening Phase was obtained after completion of the most recent line of therapy with no intervening therapies, and is less than 1 year old. The signing of the main study informed consent and collection of tumor specimen for PD-L1 testing may occur up to 56 days before the first administration of study drug. All other screening procedures must be performed only after PD-L1 results are available, and within 28 days before the first administration of study drug. For subjects who do not meet Inclusion Criterion 5, no further Screening procedures should be performed. For subjects in the randomized phase, treatment should start within 72 hours after randomization.

The inclusion and exclusion criteria for enrolling subjects in this study are described in the following 2 subsections. If there is a question about the inclusion or exclusion criteria below, the investigator must consult with the appropriate Sponsor representative and resolve any issues before enrolling a subject in the study. Waivers are not allowed.

During its review of the study data at the initial interim analysis (40 evaluable subjects), the DMC determined that the study had enrolled a sufficient number of subjects with a PD-L1 score of TC0 and recommended continued enrollment only in subjects in the TC1-3 subgroups. After this DMC recommendation, the sites were notified that only subjects with a PD-L1 score of

TC1-3 will be eligible to enroll in the study, and the protocol was amended to reflect this DMC recommendation (Section 4.1).

For a discussion of the statistical considerations of subject selection, refer to Section 11.2, Sample Size Determination.

After the third data review by the DMC, this study is closed to further enrollment.

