5. TREATMENT ALLOCATION AND BLINDING

Procedures for Randomization and Stratification

Following the safety run-in, central randomization will be implemented in this study. Subjects were stratified by PD-L1 status (TC0 and IC0 vs other), histology (squamous vs. non-squamous), and number of prior therapies received (1 vs. >1) and assigned randomly 1:1 using permuted blocks to 1 of 2 treatment groups based on a computer-generated randomization schedule prepared before the study by or under the supervision of the Sponsor. Pursuant to DMC recommendations after the first interim analysis of study data, enrollment was closed to subjects with PD-L1 score of TC0 (Section 4) as of 16 Jan 2018. Therefore, subjects will be stratified by histology (squamous vs. non-squamous), and number of prior therapies received (1 vs. >1).

The interactive web response system (IWRS) will assign a unique treatment code, which will dictate the treatment assignment and matching study drug kit for the subject. The requestor must use his or her own user identification and personal identification number when contacting the IWRS and will then give the relevant subject details to uniquely identify the subject.

As of 25 May 2018, this study was closed to further enrollment.

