11.3. Efficacy Analyses

The primary endpoint will be evaluated after approximately 90 subjects have been enrolled. The DMC will perform additional interim analyses after approximately 40 subjects and 60 subjects have had at least 1 disease assessment, respectively. These analyses will include an evaluation of efficacy as a function of PD-L1 expression. Based on these results, the DMC may recommend restricting enrollment of subjects in PD-L1 subgroups in whom clinical benefit is not demonstrated or expanding enrollment by a maximum of 100 subjects in PD-L1 subgroups without adequate enrollment (see Section 11.2) in accordance with the product label of the Ventana SP-142 assay. Study sites will be notified in writing of any changes to enrollment based on DMC recommendations.

Number and percent of subjects in each response category will be tabulated, along with those for subjects who achieve overall response (CR or PR) and who achieve disease control (ie, CBR: CR, PR, or SD with duration of at least 16 weeks). Odds ratio and its 95% confidence interval will be provided as a measure of treatment effect. Descriptive summaries (mean, standard deviation, median, and range) will be provided for time to response among those subjects who have CR or PR.

For time-to-event endpoints (PFS, OS, and duration of response), Kaplan-Meier estimates of the survival functions will be presented. For PFS and OS, Cox's regression will be performed to obtain the hazard ratio estimate and the corresponding 95% CI, which will be used as a measure for treatment effect. Additional Cox's regression may be performed to include appropriate baseline prognostic variables. Furthermore, exploratory analyses for OS may be performed to adjust for the effect of crossover. Analysis of duration of response will be performed descriptively among those subjects who achieve CR or PR.

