1.5. Randomization and Blinding

Central randomization will be implemented following the safety run-in evaluation. Subjects will be randomly assigned to 1 of 2 treatment arms based on a computer-generated randomization schedule prepared before the study by or under the supervision of the sponsor. The randomization will be balanced by using randomly permuted blocks and will be stratified by centrally determined PD-L1 expression status (TC0 and IC0 vs. others), histology (squamous vs. non-squamous), and number of prior therapies (1 vs >1).

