5.2. Primary Efficacy Endpoint

The primary efficacy endpoint is overall response rate (ORR).

Definition

The primary endpoint is overall response rate (ORR), defined as the proportion of subjects who achieve a response of partial response (PR) or better.

Analysis Methods

Analysis will be based on the ITT population, and response evaluable population. The number and percentage of subjects along with two-sided 95% exact confidence interval (CI) will be provided by treatment group in the following response categories: CR, PR, ORR, stable disease (SD), clinical benefit rate (CBR), progressive disease (PD), and not evaluable (NE).

Odds ratio of achieving response for Arm B over Arm A and its 95% confidence interval will be provided.

ORR will also be presented by the subgroups specified in Section 2.4, as appropriate.

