5.3.2. Clinical Benefit Rate

Definition

Clinical benefit rate is defined as proportion of subjects who achieve disease control (CR, PR, or SD).

Analysis Methods

Analysis will be based on the ITT population, and response evaluable population. The number and percentages of subjects achieving clinical benefit will be provided by treatment group. In addition, two-sided 95% exact CI will also be provided. Odds ratio of achieving response for Arm B over Arm A, and its 95% confidence interval will be calculated, similar to ORR.

Stratified analysis may also be performed as sensitivity analysis.

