5.3.3. Progression Free Survival

Definition

Progression-free survival (PFS) is measured from randomization until the first documented disease progression or death, whichever occurs first. PFS will be censored on the date of last tumor assessment documenting absence of tumor progression for subjects who have no documented progression and are still alive prior to data cutoff, dropout, lost to follow-up or the initiation of Subsequent anti-cancer treatment. Subjects with no tumor assessments after randomization their PFS will be censored on the date of randomization. PFS is calculated in months as follows:

$$\text{PFS} = (\text{date of PD/death or censoring} - \text{date of randomization} + 1) / (365.25/12).$$

Analysis Methods

The number and percentage of subjects who had a PFS event or were censored will be reported. The Kaplan-Meier method will be used to estimate the distribution of overall PFS for each treatment group, and the median PFS with 95% CI will be provided. In addition, the Kaplan-Meier PFS curve will also be presented by treatment group.

Hazard ratio (Arm B vs. Arm A) and its 95% confidence interval will be presented. In addition, 3, 6, 12-months of PFS rate with 95% CI will be estimated by Kaplan-Meier method and reported for each treatment group.

PFS will also be presented by the subgroups specified in Section 2.4, as appropriate.

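### Randomisation is stratified but the primary ORR odds ratio names no strata; a Mantel-Haenszel odds ratio over the two PD-L1 strata is a small, cheap improvement, not the repair of an error

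*SAP*

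**What the plan says.** - **Randomisation.** SAP 1.5 says that the randomisation "will be stratified by centrally determined PD-L1 expression status (TC0 and IC0 vs. others), histology (squamous vs. non-squamous), and number of prior therapies"; SAP 1.2 lists the same three factors. Protocol Section 5 is more recent. It says "enrollment was closed to subjects with PD-L1 score of TC0 (Section 4) as of 16 Jan 2018", and that from then on only histology and number of prior therapies are used.
- **ORR.** SAP 5.2 gives response percentages with exact confidence intervals, then: "Odds ratio of achieving response for Arm B over Arm A and its 95% confidence interval will be provided". No strata, estimator or test is named. ORR is also shown by subgroup, and SAP 2.4 defines PD-L1 there in three levels, not by the two-level randomisation split.
- **Clinical benefit rate.** SAP 5.3.2 follows the primary endpoint: "its 95% confidence interval will be calculated, similar to ORR". It then adds: "Stratified analysis may also be performed as sensitivity analysis". That sentence names no strata and has no counterpart in SAP 5.2.
- **PFS and OS.** SAP 5.3.3 and 5.3.4 each say: "Hazard ratio (Arm B vs. Arm A) and its 95% confidence interval will be presented". Protocol 11.3 names Cox regression and continues: "Additional Cox's regression may be performed to include appropriate baseline prognostic variables".
- Cochran-Mantel-Haenszel is in the SAP abbreviation list but is never used in the text.

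**The concern.** A trial that randomises within strata would usually say whether its primary effect measure uses them. Here the natural reading is a crude odds ratio, because SAP 5.3.2 models its odds ratio on the ORR one and treats stratification as an optional extra. No sentence says so outright.

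Two things are at stake, both modest. First, if PD-L1 status predicts response, as the protocol's background tables suggest, a crude analysis gives up a little precision that the IWRS data would supply free. Second, the trial is open-label, and protocol 3.4 defends that partly by fixing the primary analysis strategy before study start. An effect measure that is only implied does not fully meet that standard.

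**Working it through.** **1. The plan's own figure.** Inputs from SAP 1.4: ORR 20% vs 40%, 1:1, one-sided alpha 0.10, power 80%. The unpooled two-proportion formula gives (1.2816 + 0.8416)² × (0.20×0.80 + 0.40×0.60) / 0.20² = 4.508 × 0.40 / 0.04 = 45.1 per arm, about 90 in total. The stated figure is reproduced, and it ignores strata. The planning odds ratio is (0.40/0.60)/(0.20/0.80) = 2.67. At exactly 18/45 vs 9/45 its 95% CI is 1.04 to 6.85.

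**2. How strongly might PD-L1 predict response?** No figure in the protocol uses the randomisation split (TC0 and IC0 vs others), so these are assumptions for a range:
- Table 3, 31.6% vs 14.3%: odds ratio 2.77. Table 3, 50% vs 12.1%: 7.3.
- Table 4, second line. The columns are nested; removing the overlap gives (0.17×267 − 0.24×122)/145 = 11.1%. Then 24% vs 11.1% is an odds ratio of 2.5.
- Table 4, third line or later: (0.17×253 − 0.27×115)/138 = 8.7%. Then 27% vs 8.7% is 3.9.

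**3. Effect on power.** Simulation with 90 subjects, 1:1, permuted blocks within the eight randomisation cells and overall ORR held at 20% and 40%. The test was CMH without continuity correction at one-sided 0.10, with 40,000 runs per setting. Assumed, because the documents do not give them: blocks of 4, 30% squamous, 35% with more than one prior line (both neutral for response), and 40% PD-L1 negative while TC0 enrolment was open. Protocol Section 4 reports 40 evaluable subjects at the first interim but not the number randomised before closure, so PD-L1 varies in the first 40, the first 60 or all 90. Entries are stratified minus crude power, in percentage points (SE 0.05 to 0.09).

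| PD-L1 odds ratio | first 40 | first 60 | all 90 |
|---|---|---|---|
| 1.0 | −0.1 | −0.2 | −0.2 |
| 2.5 | +0.1 | +0.4 | +0.6 |
| 2.8 | +0.4 | +0.5 | +0.8 |
| 3.9 | +0.6 | +0.8 | +1.3 |
| 7.3 | +1.1 | +1.6 | +2.4 |

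These runs also split PD-L1 by histology when every cell held at least 5 subjects and both arms. Separate runs with the two PD-L1 strata alone gave about −0.1 at 1.0, +0.3 to +0.6 at 2.8, +1.1 at 3.9 and +2.3 at 7.3. The further split buys nothing visible. With 20% negative in the first 40, the change is −0.1 to +0.5.

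**4. A second set of assumptions.** PD-L1-negative share 15% to 40% with control ORR 8% to 14% in that group; histology and prior lines with log-odds effects of 0 or −0.7. The two-stratum estimate changes power by +0.2 to +1.2 points. One-sided error is 0.088 to 0.104 crude and 0.093 to 0.104 stratified. The standard error of the log odds ratio rises by 0.8% to 3.8%, and the median odds ratio by about 1% to 6%.

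**5. The change of quantity.** For PD-L1 odds ratios of 2.5 to 3.9 varying in the first 40 to 60 subjects, the conditional odds ratio is 2.69 to 2.81. Against 2.67 that is 2.69/2.67 = 1.01 to 2.81/2.67 = 1.05, small beside an interval of 1.04 to 6.85.

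**6. PFS and OS.** In simulations with about 25 to 75 events (assumed), unstratified and PD-L1-stratified median hazard ratios differ by at most about 0.01.

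**The case against.** The strongest reply is that the crude odds ratio is valid, matches the planning quantity, and is what the text most naturally means. On this view, swapping main and sensitivity analyses for about one point of power or less is a preference. The gain also depends on PD-L1 effects that the documents do not supply. The study behind Table 4 enrolled only TC2/3 or IC2/3 patients and so says nothing direct about TC0-and-IC0 patients. All of that stands, and it limits the size of the point. A sponsor could defensibly keep the crude odds ratio as main, provided that the SAP says so.

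A second reply is that PD-L1 alone omits histology and prior lines, the only factors in force after closure. That is true. But Table 4 shows no consistent effect of prior lines: 27% vs 24% is an odds ratio of 1.17, and 8.7% vs 11.1% is 0.76. Using all eight cells averages 90/8, about 11 subjects each. It changes power by −0.8 to +1.1 points when the other two factors are neutral and PD-L1 odds ratios run from 1.0 to 3.9. In the second set of assumptions the change is −0.1 to +1.7, with the standard error up 2% to 7.5%.

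A third reply is that a change made after the DMC has seen the data is itself post hoc. This stands, and it is why the change must be dated.

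A reader might go further and infer that the open choice inflates the error rate. Reporting the best of four stratifications would raise one-sided error from 0.10 to at most 0.106 to 0.115 for ORR. But SAP Section 5 names no test or decision rule, and nothing suggests such picking, so this bounds the latitude and does not show a fault. A reader might also infer that the PFS and OS hazard ratios are equally open. Protocol 11.3 calls models with covariates additional and SAP 5.3.3 and 5.3.4 give one plain hazard ratio, so the unstratified Cox estimate is already the plain reading.

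**Conclusion.** The point holds as a small improvement to the primary analysis. The SAP leaves the strata out of the ORR odds ratio, and using the PD-L1 strata would probably sharpen it slightly at almost no cost. The documents do not support calling the crude analysis wrong or biased, or its stated power mistaken.

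The size rests on assumed PD-L1 effects, an assumed PD-L1-negative share and an unknown number randomised before TC0 closure. Only if PD-L1 mattered as much as the sharpest contrast in Table 3 (odds ratio 7.3) would the gain reach 1.1 to 2.4 points. Because SAP Section 5 names no test, power at one-sided 0.10 serves here only as a measure of precision.

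Separately, SAP 1.2 and 1.5 are out of date against protocol Section 5, whatever is decided about the odds ratio.

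**What to change.** - **SAP 5.2, and 5.3.2 which follows it:** make the main odds ratio a Mantel-Haenszel estimate with 95% CI over the two PD-L1 strata recorded in the IWRS (TC0 and IC0 vs other). Code everyone randomised after TC0 closure as other. State that this is the randomisation split and not the three-level subgroup of SAP 2.4. Label the result a conditional odds ratio and keep the crude one as a sensitivity analysis. Use these two strata whatever the cell counts, so that the estimator is known in advance.
- **Timing:** date the change relative to the DMC reviews (the third was on 23 May 2018, with 88 subjects) and to the CSR analysis, which uses the data from that review.
- **SAP 1.2 and 1.5:** state that PD-L1 was not a stratification factor after 16 January 2018.
- **SAP 5.3.3 and 5.3.4:** as clarification only, add that the hazard ratio comes from an unstratified Cox model.

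The cost is SAP wording. Sample size, alpha and data collection do not change. The statistical price is the small power loss if PD-L1 is not prognostic, and a main odds ratio that is no longer the same quantity as the planning value. The effect on clinical benefit rate was not calculated; it is included so that 5.3.2 stays consistent with 5.2.

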5.3. Major Secondary Efficacy Endpoints

5.3.1. Duration of Response

Definition

Duration of response (DoR) is measured from date of first documented disease response to date of first objectively documented evidence of recurrence or progressive disease or death, whichever occurred first. DoR will be evaluated in subjects who have achieved response of PR or better. Duration of response is calculated in months as follows:

$$\text{DoR} = (\text{date of PD or censoring} - \text{date of first disease response} + 1) / (365.25/12),$$

Deaths due to disease progression will be treated as an event on the date of death, unless disease progression is documented before death. Subjects who start Subsequent anti-cancer treatment for NSCLC will be censored at the last disease assessment no later than the start of Subsequent anti-cancer treatments. Subjects, who are lost to follow-up, withdraw consent, withdraw from study without disease progression, or die due to causes other than disease progression will be censored at the last disease assessment date.

Analysis Methods

The Kaplan-Meier method will be used to summarize DoR for responders in each treatment group. The 25% Quantile, Median, and the 75% Quantile and their corresponding 95% CI will be provided.

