2.1.2. Endpoints

Primary Endpoint

- The primary endpoint is ORR: the proportion of subjects with a partial response (PR) or complete response (CR) as defined by RECIST 1.1

Secondary Endpoints

- Incidence of adverse events
- DoR: the duration from the date of the initial documentation of a response to the date of the first objectively documented evidence of recurrence or progressive disease or death, whichever status is recorded first.
- CBR: the proportion of subjects who achieve disease control (CR, PR, or SD with duration of at least 16 weeks).
- PFS: the duration from the date of randomization to the date of objectively documented progression or death due to any cause, whichever status is recorded first.
- OS: the duration from the date of randomization to the date of death due to any cause.
- Serum daratumumab concentration (C_{min} , C_{max}) and incidence of anti-daratumumab antibodies
- Serum atezolizumab concentration (C_{min} , C_{max}) and incidence of anti-atezolizumab antibodies

Exploratory Endpoints

- ORR_i: the proportion of subjects with a partial response (PR) or complete response (CR) evaluated by irRECIST
- ORR, DoR, CBR, incidence of adverse events, daratumumab and atezolizumab serum concentration and incidence of anti-daratumumab antibodies and anti-atezolizumab antibodies

Refer to Section 9, Study Evaluations for evaluations related to endpoints.

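### SAP 5.3.1 is internally inconsistent on duration of response: its new-therapy censoring sentence does not exclude responders whose progression is already documented

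*SAP*

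**What the plan says.** Protocol 2.1.2 ends DoR at "the first objectively documented evidence of recurrence or progressive disease or death, whichever status is recorded first". SAP 5.3.1 opens with the same definition, running from first response "to date of first objectively documented evidence of recurrence or progressive disease or death, whichever occurred first", and its formula uses the date of progression or of censoring.

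The same SAP paragraph then gives operational rules:

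- **Death from progression** is an event on the date of death, except where progression was documented earlier.
- **New therapy:** "Subjects who start Subsequent anti-cancer treatment for NSCLC will be censored at the last disease assessment", meaning the latest one on or before the day that treatment begins.
- **Other exits:** the rule for responders who "withdraw from study without disease progression, or die due to causes other than disease progression will be censored at the last disease assessment date" also covers loss to follow-up and withdrawal of consent.

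The PFS rule in SAP 5.3.3 also censors at new therapy, but it applies only "for subjects who have no documented progression and are still alive prior to data cutoff, dropout, lost to follow-up" or the start of subsequent treatment. The scan used for PFS censoring must itself show no progression.

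Protocol 11.3 says DoR is analysed descriptively among responders. SAP 5.3.1 plans Kaplan-Meier quartiles and no test.

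**The concern.** The new-therapy sentence covers every responder who starts subsequent treatment. Unlike the PFS rule, it does not say that progression must not already have been documented, and it does not say that the scan on which the responder is censored must be free of progression.

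This matters because of the usual order of events. Protocol 8.2 prohibits other cancer therapy during study treatment until progression has been documented and study treatment has stopped. Progression followed by new therapy is therefore the expected sequence. For that patient, the definition gives an event and the operational sentence, taken at its word, gives a censored time. Nothing in either document says which prevails. If the sentence is coded literally, the events that define the endpoint are removed and responses look more durable than they were.

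**Working it through.** **1. The plan's own figure.** No number is attached to the DoR rule. The only computable design figure is the sample size (SAP 1.4): 20% against 40%, 1:1, one-sided alpha 0.10, 80% power, 90 subjects. With unpooled variance, n per arm = (0.2×0.8 + 0.4×0.6)(1.2816 + 0.8416)² / 0.2² = 0.40 × 4.508 / 0.04 = 45.08, or 90.2 in total. Power at 45 per arm is 79.9% (79.0% with pooled variance). The figure reproduces and does not depend on DoR. It is used here only for the expected number of responders: 45 × 0.20 = 9 in Arm A and 45 × 0.40 = 18 in Arm B.

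**2. The rules side by side.**

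| Rule | Requires no earlier progression? | Requires a progression-free censoring scan? |
|---|---|---|
| DoR, death from progression (5.3.1) | Order of events is stated | Not applicable |
| DoR, new therapy (5.3.1) | No | No |
| DoR, withdrawal from study (5.3.1) | Yes | No |
| PFS, new therapy (5.3.3) | Yes | Yes |

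**3. One invented responder, on the 6-weekly scan schedule.** First response at week 12, progression on the week-30 scan, a repeat scan at week 36 (protocol 9.4.2 and Table 12 provide for repeat imaging at least 4 weeks after first progression), and new therapy after week 36 but before the next scan.

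- By the definition: event at week 30. DoR = (18×7 + 1) / 30.4375 = 127 / 30.4375 = 4.2 months.
- By the new-therapy sentence, literally: censored at the last assessment before new therapy, week 36. DoR = (24×7 + 1) / 30.4375 = 169 / 30.4375 = 5.6 months, no event.
- By the logic of the PFS rule: event at week 30.

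The literal rule removes the event and can also credit time after progression.

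**4. Direction and size.** Let f be the share of progressing responders who start new therapy. The documents give no value, so f is an assumption, shown over a range. Suppose that all events are progressions, that f is the same at all times, and that the censoring scan is the progression scan. The apparent hazard is then (1−f) times the true one, and the apparent curve is S(t)^(1−f), which is never below S(t).

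| f | Progression events kept | Of 9 / of 18, if all responders progress | Apparent curve at the true median (truth 50%) |
|---|---|---|---|
| 0.25 | 75% | 6.75 / 13.5 | 0.5^0.75 = 59% |
| 0.50 | 50% | 4.5 / 9 | 0.5^0.50 = 71% |
| 0.75 | 25% | 2.25 / 4.5 | 0.5^0.25 = 84% |

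With 9 responders, one event at full risk set moves the curve by 1/9 = 11 percentage points. With 18 it is 1/18 = 5.6 points. A few recoded events would therefore shift the reported quartiles.

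**The case against.** The best defence is that a responder with documented progression has already reached the endpoint, so later therapy leaves nothing to censor. The definition says that the first event counts, the formula uses the progression date, and the limit to assessments no later than the start of new therapy reads as a cut-off of follow-up. No passage says that a documented progression is to be discarded. The missing condition also looks like loose drafting: in the next sentence, the no-progression qualifier attaches only to study withdrawal, and loss to follow-up and withdrawal of consent lack it too.

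Most of this stands. Progression-first is the probable intent, and a careful programmer may well code it so. It does not settle the matter, because the same paragraph overrides its own definition elsewhere: the definition counts any death, yet responders who "withdraw from study without disease progression, or die due to causes other than disease progression will be censored at the last disease assessment date". A programmer cannot assume that the definition wins over the operational sentences.

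Four stronger readings are tempting and are not supported.

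- **That the plan does discard documented progressions.** This follows only from literal coding of one sentence against the definition beside it.
- **That medians of 24, 34 or 57 months would be reported.** These come from dividing the 17-month median in protocol 1.2 by (1−f), with f = 30%, 50% and 70%. The 17 months belongs to a separate Phase 1 study and the f values are assumed. From the first protocol (25 July 2016) to the May 2018 review on which the study report rests is 667 days, about 22 months, so such medians could not be observed.
- **That the arms would show a DoR hazard ratio of 2.0.** This needs assumed shares of 70% in Arm A and 40% in Arm B (0.6/0.3 = 2.0), and no DoR hazard ratio is planned.
- **That Arm A is hit harder through crossover.** This requires crossover to be coded as subsequent anti-cancer treatment. Protocol 4.3.2 (criterion 1X) distinguishes subsequent therapies from study drug given after crossing over, and SAP 5.1.2 treats crossover data as something that may be summarized separately.

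**Conclusion.** The point holds as an internal inconsistency in SAP 5.3.1. For a responder who progresses and then starts new therapy, the definition yields an event and the new-therapy sentence, read literally, yields a censored time. The PFS rule carries both missing limits. If the sentence is programmed as written, DoR is overstated. By how much depends on an unknown share of progressors receiving new therapy. The table in the working shows a range under stated assumptions and is not a forecast for this trial.

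The reach is limited. DoR is a descriptive secondary endpoint with about 9 and 18 expected responders and no test or decision rule. The ORR analysis, the sample size of 90 and the power do not change. Comparing DoR between arms is nevertheless a stated secondary objective, and with so few responders the coding choice could be visible in the reported quartiles.

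**What to change.** Replace the new-therapy sentence in SAP 5.3.1 with:

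*Responders who start subsequent anti-cancer treatment before documented progression or death will be censored at the last disease assessment showing no progression on or before that start; progression documented on or before the start of subsequent treatment is an event.*

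This agrees with protocol 2.1.2 and brings DoR into line with the PFS rule in SAP 5.3.3. If the DoR derivation is already programmed, confirm which rule was coded. The cost is one sentence and a check or small change to the program, with no new data. The downside is that reported DoR may be shorter than under the literal rule.
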